10.2.1. Calculation or Derivation of Pharmacokinetic Parameters

The derivation of PK parameters from the serum concentration-time data of the individual mAbs AZD8895 and AZD1061, as well as for the sum of the individual mAbs of AZD7442 (AZD8895 + AZD1061) will be performed by LabCorp, on behalf of Clinical Pharmacokinetic Alliance, AstraZeneca R&D.

PK parameters will be derived using non-compartmental methods with Phoenix® WinNonlin® Version 8.1, or higher.

PK analysis will, where data allow, be carried out using actual elapsed times determined from the PK sampling and dosing times recorded in the raw data. If actual elapsed times are missing, nominal times will be used.

10.3. CCI

CCI

10.4. Immunogenicity Variables

The date and time of the blood samples collected for assessment of ADAs (samples to confirm the presence or absence of anti-AZD8895 and anti-AZD1061 antibodies from pre-dose Day 1 to Day 361, including the titer for samples confirmed positive for ADA) and neutralizing Abs will be listed. The incidence of ADA to AZD7442 will be summarized as number and percentage of participants who are ADA positive by treatment group.

11. STATISTICAL METHODS AND SAMPLE SIZE DETERMINATION

11.1. Description of Analysis Sets

11.1.1. General Principles

A separate SAP will be compiled for this study. The details of the formal hypothesis testing will be detailed in the SAP.

Regarding PK comparability, if the 90% CIs for the geometric mean ratios for both AUCinf (AUClast for some agencies) and Cmax are entirely contained within 0.8000 and 1.2500 for all comparisons according to the study objectives, it may be concluded that the 2 formulations (the co-formulation and the formulation from the individual vials) are comparable and the 2 materials (clonal cell line material and cell pool material) are comparable.

11.1.2. Safety Analysis Set

The safety analysis set will include all participants who were randomized and received any amount of IMP.

Unless otherwise stated, the safety analysis set will be used for the presentation of all demographic and disposition data, safety analyses, as well as any immunogenicity assessments. Exposure to IMP will also be presented using the safety analysis set.

11.1.3. Pharmacokinetic Analysis Set

The PK analysis set will consist of all participants in the safety analysis set who received IMP and have evaluable serum PK data, with no important protocol deviations thought to impact on the analysis of the PK data.

Data from participants for whom the pre-dose concentration is > 5% of their respective Cmax for AZD8895 or AZD1061 may be excluded from the summary tables and figures and from the statistical analysis.

The exclusion of any participants from summary tables and figures and from the statistical analysis or exclusion of any time points from the calculation of the PK parameters will be documented by the PK Scientist including the reason(s) for exclusion.

The available concentration data and PK parameter data for any participants excluded from the statistical analysis will be listed only. Concentration data for participants excluded from the statistical analysis will be presented in the individual figures of concentration versus time plots.

11.1.4. Pharmacodynamic Analysis Set

All participants in the safety analysis set who received IMP and have evaluable CCI [REDACTED] data, with no important protocol deviations thought to impact the analysis of CCI [REDACTED]

11.1.5. Randomized Set

The Randomized Set will consist of all participants randomized into the study.

11.2. Methods of Statistical Analyses

11.2.1. General Principles

The statistical methodology below describes the statistical analysis as it is foreseen when the study is being planned.

If circumstances should arise during the study rendering the analysis inappropriate, or if in the meantime improved methods of analysis should come to light, different analyses may be performed.

A SAP will be written for the study. Any deviations from the statistical methodology defined in this protocol or SAP, reasons for such deviations and all alternative/additional statistical analyses that may be performed will be described in the CSR. Such changes to analyses may be written into an abbreviated SAP, if appropriate. The verification and review of all statistical modeling assumptions will be documented appropriately.

All original and derived parameters as well as demographic and disposition data will be listed and described using summary statistics. All safety data (scheduled and unscheduled) will be presented in the data listings.

Demographic and baseline data will be summarized for all randomized participants by treatment group (Treatment Groups A, B, and C and Total). Pharmacokinetic data will be summarized by treatment group, treatment group and injection site, treatment group and bodyweight category, and treatment group, injection site, and bodyweight category. Safety and tolerability data will be summarized by treatment group (Treatment Groups A, B, and C and Total), if applicable.

Frequency counts (number of participants [n] and percentages) will be calculated for each qualitative variable. Descriptive statistics (n, mean, SD, median, minimum and maximum) will be calculated for each quantitative variable (unless otherwise stated). Descriptive statistics will only be presented if $n \geq 3$. If no participants have data at a given time point, then only $n = 0$ will be presented. If $n < 3$, only the n, minimum and maximum will be presented, and if $n = 3$, only the n, median, minimum and maximum will be presented; the other descriptive statistics will be left blank.

The following rules will apply to any repeated safety assessments occurring within each treatment group:

- If the repeated measurement of a specific parameter occurs prior to IMP administration (Day 1), then the last obtained value prior to dosing will be used in the descriptive statistics and in the calculation of changes from baseline.
- If the repeated measurement of a specific parameter occurs after IMP administration (Day 1), then the first (non-missing) value after dosing will be used in descriptive statistics and in the calculation of changes from baseline.

The planned sequence for measurement of multiple assessments at the same time point is described in Section [3.1.1](#).

For safety assessments performed at screening and the follow-up, the following rules will apply for any repeated assessments:

- If the repeated assessment occurs at screening the last available value will be used in the summary statistics.
- If the repeated assessment occurs at the Follow-up Visit the first non-missing assessment will be used in the summary statistics.

All statistical analyses and production of tables, figures and listings will be performed using SAS® version 9.4 or later.

11.2.2. Missing Data

Missing dates and times in the AE data will be handled as described in Section [10.1](#). Concentrations that are NQ in the PK data will be handled as described in Section [10.2.1](#).

There will be no imputations of other missing data. All participants will be included into the safety analyses as far as the data permit.

11.2.3. Participant Characteristics

A randomization listing will be presented and include the following: each participant's randomization number, the participant's full enrollment number, the treatment to which the participant has been randomized and the country where the study Clinical Unit is located.

Participants and/or data excluded from the PK analysis set will be listed including the reason for exclusion. Participant disposition will be summarized and will include the following information: number of participants randomized and dosed, number and percentage of participants completing the study and the number and percentage of participants who were withdrawn (including reasons for withdrawal). Disposition data will be presented based on all participants randomized.

Participant discontinuations will be listed including the date of study exit, duration of treatment and reason for discontinuation. A listing of informed consent response will also be presented.

11.2.3.1. Demographic and Baseline Data

Demographic variables (age, gender, race, ethnicity, height, weight, and BMI) will be listed by participant. Demographic characteristics (age, gender, race and ethnicity) and participant characteristics (height, weight, and BMI) will be summarized separately for all randomized participants by treatment group (Treatment Groups A, B, and C and Total). The denominator for percentages will be the number of randomized participants.

Medical history data will be listed by participant including visit, description of the disease/procedure, MedDRA SOC, MedDRA PT, start date and stop date (or ongoing if applicable).

11.2.4. Prior and Concomitant Medication and Drug Administration

11.2.4.1. Prior and Concomitant Medication

Prior medications are those that started and stopped prior to the first dose of IMP; all medications taken after first dosing are considered as concomitant (including medications that started prior to dosing and continued after). Prior medications started within 3 months prior to the first dose of IMP and last dose of anti-COVID-19 vaccine received prior to randomization will be recorded also in the concomitant medication module of the EDC system.

Prior and concomitant medication will be listed by participant and will include the following information: reported name, preferred term, the route of administration, dose, frequency, start date/time, duration, and indication. Prior and concomitant medication will be coded according to the AstraZeneca dictionary.

The duration of the medication will be calculated as:

$$\text{Duration} = (\text{end date/time}) - (\text{start date/time}) + 1$$

The duration may be presented in hours or days in the listing depending on the applicability to the emerging data. For medications with partial or completely missing start date/times and/or end date/times, the duration will not be calculated.

Medications with missing or partial start date/time and/or end date/time such that it is not possible to classify as prior or concomitant will be considered as concomitant in the listings.

11.2.4.2. IMP Administration

The IMP administration dates and times will be listed for each participant.

11.2.5. Safety and Tolerability

All safety data (scheduled and unscheduled) will be presented in the data listings sorted by treatment group and participant. Continuous variables will be summarized using descriptive statistics (n, mean, SD, min, median, max) by treatment group (Treatment Groups A, B, and C and Total). Categorical variables will be summarized in frequency tables (frequency and proportion) treatment group (Treatment Groups A, B, and C and Total).

The analysis of the safety variables will be based on the safety analysis set.

Adverse events will be summarized by SOC and PT using MedDRA vocabulary. Furthermore, listings of SAEs and AEs leading to withdrawal will be made and the number of participants who had any AEs, SAEs, AEs leading to withdrawal, and AEs with severe intensity will be summarized. Adverse events that occur before dosing will be reported separately.

Tabulations and listings of data for vital signs and clinical laboratory tests, and listings for ECGs will be presented. Any new or aggravated clinically relevant abnormal medical physical examination finding compared to the baseline assessment will be reported as an AE. Data will be summarized for the observed values at each scheduled assessment, together with the corresponding changes (and/or percentage change) from the baseline when baseline is defined. Clinical laboratory data will be reported in Système International units in the CSR.

Out-of-range values for safety laboratory will be flagged in individual listings as well as summarized descriptively using agreed reference standard reference ranges and/or extended reference ranges (eg, AstraZeneca, program, or laboratory ranges).

11.2.6. Pharmacokinetics

The serum concentrations and PK parameters for the individual mAbs AZD8895 and AZD1061, as well as for the sum of the individual mAbs of AZD7442 (AZD8895 + AZD1061), will be listed and presented in tabular and graphical form as appropriate according to the most recent version of the AstraZeneca Clinical Pharmacology Expertise tables, listings, and figures standards, that includes applicable descriptive statistics, handling of individual serum concentrations below the lower limit of quantification for listings, descriptive statistics and figures, and precision and rounding rules for concentrations and PK parameter data.

11.2.6.1. Serum Concentration Data

For the individual mAbs AZD8895 and AZD1061, as well as for the sum of the individual mAbs of AZD7442 (AZD8895 + AZD1061), the serum concentrations for each scheduled time point will be summarized by treatment group, treatment group and injection site, treatment group and bodyweight category, and treatment group, injection site, and bodyweight category using appropriate descriptive statistics, based on the PK analysis set. A listing of all

concentration-time data, ie, PK scheduled times, actual sample collection times, sample actual relative times, as well as derived sampling time deviations will be presented by treatment group (with injection site, and bodyweight category listed) for all participants in the safety analysis set.

11.2.6.2. Serum Pharmacokinetic Parameter Listings

All reportable PK parameters for the individual mAbs AZD8895 and AZD1061, as well as for the sum of the individual mAbs of AZD7442 (AZD8895 + AZD1061), including individual diagnostic and λ_z -related parameters, will be listed for each participant by treatment group (with injection site, and bodyweight category listed) based on the safety analysis set.

11.2.6.3. Serum Pharmacokinetic Parameter Descriptive Statistics

All PK parameters for the individual mAbs AZD8895 and AZD1061, as well as for the sum of the individual mAbs of AZD7442 (AZD8895 + AZD1061) will be summarized by treatment group, treatment group and injection site, treatment group and bodyweight category, and treatment group, injection site, and bodyweight category using appropriate descriptive statistics, based on the PK analysis set.

11.2.6.4. Graphical Presentation for Serum Concentration Data

Individual serum concentration-time data will be graphically presented on linear and semi-logarithmic scales, for all participants in the safety analysis set. Combined individual serum concentration versus actual times will be plotted on both the linear and semi-logarithmic scale for all participants in the PK analysis set. Plots will be grouped by treatment group. Figures for the geometric mean (\pm gSD) serum concentration-time data will be presented by treatment group, treatment group and injection site, treatment group and bodyweight category, and treatment group, injection site, and bodyweight category, on both a linear and semi-logarithmic scale (no gSD presented), for all participants in the PK analysis set.

11.2.6.5. Graphical Presentation for PK Parameter Data

For the individual mAbs AZD8895 and AZD1061, as well as for the sum of the individual mAbs of AZD7442 (AZD8895 + AZD1061), individual PK parameter with geometric mean (95% CI) for Cmax, AUClast, and AUCinf, will be graphically presented by treatment group, treatment group and injection site, treatment group and body weight category, and treatment group, injection site and body weight category for all participants in the PK analysis set.

11.2.6.6. Statistical Analysis for Pharmacokinetic Comparability

Pharmacokinetic comparability will be assessed between Treatment A versus Treatment B, Treatment A versus Treatment C, and Treatment B versus Treatment C based on the PK analysis set.

Analyses will be performed using a linear fixed effects analysis of variance model using the natural logarithm of primary PK parameters (eg, AUCinf, AUClast, and Cmax) for the individual mAbs AZD8895 and AZD1061, as well as for the sum of the individual mAbs (AZD8895 + AZD1061) as the response variables, treatment, injection site, anti-COVID-19 vaccination status, and continuous baseline body weight on the log scale as fixed effects and participant as a random effect. Transformed back from the logarithmic scale, geometric means together with CIs (2-sided 95%) for AUCs and Cmax will be estimated and presented. Also, ratios of geometric means together with CIs (2-sided 90%) will be estimated and presented.

11.2.7. Pharmacodynamics

11.2.7.1. CCI

CCI

11.2.8. Immunogenicity Assessment

The date and time of the blood samples collected for assessment of ADAs (samples to confirm the presence or absence of anti-AZD8895 and anti-AZD1061 antibodies from pre-dose Day 1 to Day 361, including the titer for samples confirmed positive for ADA) and neutralizing Abs will be listed. Tabulations will be provided for each treatment group. The analyses will be based on the safety analysis set.

The results of the ADA assessments will be listed for each participant and time point. This will include the classification of the response (positive/negative) and the measured titers where appropriate. Summary tables will be presented, by treatment group, for the number and percentage of participants with positive/negative results at each time point. The analyses will be based on the safety analysis set.

The impact of ADA on PK, and association with AEs and SAEs may be assessed.

11.3. Protocol Deviations

Protocol deviations are considered as any deviation from the CSP relating to a participant, and include the following:

- Inclusion/exclusion criteria deviations
- Dosing deviations (eg, incorrect treatment received, participant was not fasted as per the protocol requirements prior to and after dosing)
- Time window deviations for safety and/or PK assessments
- Participants receiving prohibited concomitant medications
- Other procedural and study conduct deviations recorded by the study Clinical Unit on a protocol deviation log

The criteria for the assessment and reporting of protocol deviations will be stipulated in a separate study specific protocol deviation specification document. This will include a WAD which stipulates tolerance windows for safety and PK assessments. Measurements performed within these tolerance windows will not be considered as protocol deviations and will not be reported.

All protocol deviations will be discussed at the data review meeting prior to database hard lock in order to define the analysis sets for the study.

Important protocol deviations will be listed by participant.

Protocol deviations will be handled in accordance with Parexel SOPs.

For handling of protocol amendments, see Section 8.1.

11.4. Determination of Sample Size

Preliminary analysis of PK data from the first-in-human study, D8850C00001, indicated that after an IM dose of IMP (separate AZD8895 and then AZD1061 doses) at a dose of 300 mg total protein, the CV% for Cmax of the individual mAbs, AZD8895 and AZD1061 were 35.6% and 38.5%, respectively, while the CV% for AUCs of both individual mAbs, AZD8895 and AZD1061 were < 36.4%. Therefore, assuming a mean ratio of 1 between comparators, 69 participants per group will provide at least 95% power to demonstrate comparability (90% CI contained within 0.8 and 1.25).

Table 11-1 Preliminary Pharmacokinetic data from Study D8850C00001

	AZD8895	AZD1061
Cmax	35.6%	38.5%
AUC0-last	29.1%	30.4%
AUC0-inf	26.8%	36.4%

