- To evaluate the PK comparability between AZD7442 administered as a single IM dose (co-formulation) (AZD8895 + AZD1061) and two separate IM doses (AZD8895 and then AZD1061) (clonal cell line material of AZD8895 and AZD1061) of the individual mAbs in healthy adult participants.
- To evaluate the PK comparability between AZD7442 administered as a single IM dose (co-formulation) (AZD8895 + AZD1061) and two separate IM doses (AZD8895 and then AZD1061) (cell pool material of AZD8895 and AZD1061) of the individual mAbs in healthy adult participants.
- To evaluate the PK comparability between the clonal cell line material and the cell pool material of AZD7442 administered as two separate sequential IM doses (AZD8895 and then AZD1061) of the individual mAbs in healthy adult participants.

Secondary Objectives:

- To examine the serum PK profiles of AZD7442 when administered as a single IM dose (co-formulation) (AZD8895 + AZD1061) and as two separate IM doses (AZD8895 and then AZD1061) (clonal cell line or cell pool material) of the individual mAbs in healthy adult participants.
- To further assess the safety of AZD7442 when administered as a single IM dose (co-formulation) (AZD8895 + AZD1061) and as two separate IM doses (AZD8895 and then AZD1061) (clonal cell line or cell pool material) of the individual mAbs in healthy adult participants.
- To evaluate the anti-drug-antibody (ADA) responses to AZD7442 in serum following administration as a single IM dose (co-formulation) (AZD8895 + AZD1061) and as two separate IM doses (AZD8895 and then AZD1061) (clonal cell line or cell pool material) of the individual mAbs in healthy adult participants.

Exploratory Objective:

- CCI

Study Design

This is a randomized, open label, three-arm, single dose, parallel group, multi-center, PK comparability study. A total of 207 evaluable healthy male and female participants will be randomized in a 1:1:1 ratio between the 3 treatment groups (69 participants per group). Each participant will receive AZD7442 as either a single IM dose (co-formulation; AZD8895 + AZD1061), or as two separate IM doses of the individual mAbs (AZD8895 and then AZD1061) from either clonal cell line material or cell pool material.

Treatment Groups:

- **Treatment A:** 300 mg (total protein) AZD7442 as a single IM dose (co-formulation of 150 mg AZD8895 + 150 mg AZD1061) (clonal cell line material).

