On the day of IMP administration (Day 1), participants should follow a diet, which excludes all alcohol (from at least 72 hours prior to dosing) and caffeinated products (from at least 24 hours prior to dosing). Participants are not required to abstain from food and drink intake until 45 minutes to 1 hour before IMP administration.

Expected Duration of the Study

The total duration of the study for a participant will be approximately 389 days comprising of a Screening Period that can last up to 28 days, Treatment Period of 1 day, and a Follow-up Period of 360 days.

Targeted Study Population

This study will be conducted in healthy volunteers, who may be male or female, ≥ 18 years of age, weighing ≥ 50 to ≤ 110 kg, and with a body mass index of ≥ 18 to ≤ 30 kg/m².

Participants should be either non-vaccinated against SARS-CoV-2 infection or vaccinated with the last vaccine dose received at least 14 calendar days before IMP dose. Participants will be allowed to receive anti-COVID-19 vaccination during the study, however, should wait 14 days after their dose of IMP. Participant vaccination status will be documented throughout the study in the eCRF.

All participants must have negative results for SARS-CoV-2 RT-PCR test ≤ 3 days prior to randomization or negative results for rapid SARS-CoV-2 antigen test on day of randomization. Participants with a medical history of infection with SARS or Middle East Respiratory Syndrome or with any clinical signs or symptoms consistent with COVID-19 will be excluded from the study.

Outcome Endpoints

Safety Endpoints:

Safety variables will include

- AEs and SAEs.
- Vital signs (systolic and diastolic blood pressure and pulse rate).
- 12-lead ECGs.
- Physical examination.
- Laboratory assessments (hematology, clinical chemistry, and urinalysis).

Viral serology, drugs of abuse and alcohol will be assessed for eligibility. Coagulation, FSH (to confirm postmenopausal status for female participants) and pregnancy testing (for all female participants of childbearing potential), and use of concomitant medication will also be assessed and reported.

Pharmacokinetic Endpoints:

Where possible, PK parameters will be assessed from serum concentrations for the individual mAbs AZD8895 and AZD1061, as well as for the sum of the individual mAbs (AZD8895 + AZD1061), referred to as AZD7442.

- Primary PK parameters: AUCinf, AUClast, and Cmax.

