3. STUDY DESIGN

3.1. Overall Study Design and Flow Chart

This study will be an open label, randomized, three-arm, parallel group, single dose, study in healthy participants (males and females), performed at multiple study centers.

A total of 207 evaluable healthy male and female participants will be randomized in a 1:1:1 ratio between the three treatment groups (69 participants per group). Each participant will receive AZD7442 as either a single IM dose (co-formulation; AZD8895 + AZD1061) from a single vial or as two separate IM doses of the individual mAbs (AZD8895 and then AZD1061) from two separate vials from either clonal cell line material or cell pool material as follows:

- **Treatment A:** 300 mg (total protein) AZD7442 as a single IM dose (co-formulation of 150 mg AZD8895 + 150 mg AZD1061) (clonal cell line material).
- **Treatment B:** 300 mg (total protein) AZD7442 as two separate IM doses of the individual mAbs (150 mg AZD8895 and then 150 mg AZD1061) (clonal cell line material).
- **Treatment C:** 300 mg (total protein) AZD7442 as two separate IM doses of the individual mAbs (150 mg AZD8895 and then 150 mg AZD1061) (cell pool material).

The product in Treatment Groups A and B is derived from material that originated from a clonal cell line, with a separate cell line, GMP cell bank, and manufacturing process for AZD8895 and AZD1061. The product in Treatment Group C is derived from material that originated from a non-clonal cell pool, with a separate pool of cells, GMP cell bank, and manufacturing process for AZD8895 and AZD1061. The clonal cell line is derived from a subpopulation of the respective cell pool, and there are no differences in antibody sequence between these cell banks. These materials have been demonstrated to be analytically comparable to each other. Refer to [Table 5-1](#) for details on the IMP.

Additionally, within each of the treatment groups, participants will be randomized 1:1:1 to one of the three injection sites:

- Lateral thigh,
- Gluteal dorsal,
- Gluteal ventral.

Further, participants will be stratified based on the body weight and vaccination status at randomization as follows:

[figure not shown]
- Body weight at randomization: < 70 kg; 70 to < 80 kg; and \geq 80 kg
- Anti-SARS-CoV-2 vaccination status at randomization: non-vaccinated or vaccinated (with one or more locally approved/authorized COVID-19 vaccine doses)

The study will comprise of:

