3.3.2. Clinical Pharmacokinetics

Measured serum AZD8895 and AZD1061 concentrations support that the PK of these mAbs are similar to each other and are consistent with what has been observed for another IgG1 κ mAb that has been engineered to include YTE amino acid substitutions to extend the half-life ([Griffin et al 2017](#)). Therefore, the half-life of AZD7442 is estimated to be approximately 90 days which will allow for long-term protection.

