4.10.4 Primary Endpoint

The primary endpoints for evaluation of pharmacokinetic comparability will be assessed using a linear fixed effects analysis of variance model with the natural logarithm of primary PK parameters (eg, AUCinf [for final analysis only], AUClast, Cmax and AUC0-91d [for IA only]) for the individual mAbs AZD8895 and AZD1061, as well as for the sum of the individual mAbs of AZD7442 (AZD8895 + AZD1061) as the response variables, treatment, injection site, anti-COVID-19 vaccination status (as reported on the CRF), and continuous baseline body weight on the log scale as fixed effects and participant as a random effect.

Transformed back from the logarithmic scale, geometric least square means (GLSM) together with CIs (2-sided 95%) will be estimated and presented by treatment. Also, ratios of geometric least square means together with CIs (2-sided 90%) will be estimated and presented.

The following treatment comparisons will apply:

- Treatment A vs Treatment B
- Treatment A vs Treatment C
- Treatment B vs Treatment C

where:

- Treatment A: 300 mg (total protein) AZD7442 as a single IM dose (co-formulation of 150 mg AZD8895 + 150 mg AZD1061) (clonal cell line material).

- Treatment B: 300 mg (total protein) AZD7442 as two separate IM doses of the individual mAbs (150 mg AZD8895 and then 150 mg AZD1061) (clonal cell line material).
- Treatment C: 300 mg (total protein) AZD7442 as two separate IM doses of the individual mAbs (150 mg AZD8895 and then 150 mg AZD1061) (cell pool material).

One statistical model will be fitted for each PK parameter, including all study data. Estimating parameters for the comparisons listed above will be done from this one model making use of the appropriate contrasts.

A variance component covariance structure will be used for the within-participant errors. Degrees of freedom will be determined using Kenward-Roger approximation.

If the estimating algorithms do not converge, these covariance structures will be tried: first-order autoregressive, compound symmetry, unstructured and Toeplitz.

Missing values will not be imputed. In this analysis it is thus assumed that any missing values are missing at random (MAR).

The following figures, in black and white, will be generated:

Figure	Analysis set	Presented by

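### The stated power of at least 95% is at best a per-parameter, per-comparison figure (about 94% for AZD1061 Cmax); it is not the power of the all-comparisons rule

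*Protocol*

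**What the plan says.** Protocol 11.4 gives coefficients of variation from the first-in-human study, assumes a mean ratio of 1, and concludes that "69 participants per group will provide at least 95% power to demonstrate comparability (90% CI contained within 0.8 and 1.25". The same sentence stands in the synopsis and in SAP 4.12. It does not name the parameter, the analyte or the number of comparisons that the power refers to.

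Protocol 11.1.1 sets the condition for concluding comparability. The 90% CIs for AUCinf (AUClast for some agencies) and for Cmax must be such that they "are entirely contained within 0.8000 and 1.2500 for all comparisons according to the study objectives". Protocol 11.2.6.6 lists three comparisons: A versus B, A versus C and B versus C.

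The rule names no analyte. The primary objectives are worded for AZD7442 ("To evaluate the PK comparability between AZD7442 administered as a single IM dose (co-formulation"), and the synopsis uses that name for the sum: "as well as for the sum of the individual mAbs (AZD8895 + AZD1061), referred to as AZD7442". The analysis in 11.2.6.6 is nevertheless specified "for the individual mAbs AZD8895 and AZD1061, as well as for the sum of the individual mAbs (AZD8895 + AZD1061) as the response variables".

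**The concern.** The power sentence speaks of demonstrating comparability, and 11.1.1 defines when comparability may be concluded. A reader who joins the two will take 95% as the chance that the study meets its own rule when the products are identical. The calculation appears to cover a single interval, whereas the rule asks for several intervals at once, and one of the CVs named in 11.4 looks slightly too large even for a single interval.

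What is at stake is how a failed interval is interpreted. Every interval has to pass, so one chance miss blocks the conclusion. Anyone judging whether a marginal miss is chance or a real difference needs the correct baseline power.

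**Working it through.** **Inputs**
- CVs (AZD8895 / AZD1061), Protocol Table 11-1: Cmax 35.6% / 38.5%; AUClast 29.1% / 30.4%; AUCinf 26.8% / 36.4%.
- True ratio 1; limits 0.80 and 1.25; two-sided 90% CI, equivalent to two one-sided tests at 5% each.
- 69 evaluable per group, from Protocol 3.1: "A total of 207 evaluable healthy male and female participants will be randomized in a 1:1:1 ratio".
- Assumptions made here: the CVs are residual variability, and covariates bring no gain. Protocol 11.4 says neither.

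**Step 1: the plan's own figure, one parameter in one comparison.** Log-scale SD s = sqrt(ln(1 + CV²)); standard error of the log ratio SE = s × sqrt(2/69); limit ln 1.25 = 0.2231.

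For AZD1061 Cmax, s = sqrt(ln(1 + 0.385²)) = 0.3718 and SE = 0.3718 × 0.1702 = 0.0633. The normal approximation is 2Φ(0.2231/0.0633 − 1.645) − 1 = 2Φ(1.88) − 1 = 94.0%. Integrating over the distribution of the variance estimate gives 93.75% with 136 df (two arms) and 93.84% with 204 df (three arms pooled).

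The stated 95% is therefore reproduced to within about a point as a single-interval figure.

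**Step 2: all three comparisons, one parameter.** All three pairwise intervals lie within the limits exactly when the range of the three arm means on the log scale plus the CI half-width is below 0.2231. This uses the pooled variance (204 df) and was checked by simulation of 400,000 trials.

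| Parameter | s | One comparison (df 136 / 204) | All three comparisons |
|---|---|---|---|
| AZD1061 Cmax | 0.3718 | 93.75 / 93.84% | 85.3% |
| AZD1061 AUCinf | 0.3527 | 95.99 / 96.05% | 90.2% |
| AZD8895 Cmax | 0.3454 | 96.69 / 96.74% | 91.8% |
| AZD1061 AUClast | 0.2973 | 99.39 / 99.40% | 98.4% |
| AZD8895 AUClast | 0.2851 | 99.66 / 99.67% | 99.1% |
| AZD8895 AUCinf | 0.2634 | 99.91 / 99.91% | 99.7% |

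For A-B and A-C only, AZD1061 Cmax has about 88.9%.

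**Step 3: from one parameter to the rule.** Adding requirements cannot raise the probability that all are met. If each mAb must pass, the smallest entry in the last column, 85.3%, is therefore an upper limit on the unadjusted power of the rule, with AUCinf or with AUClast. No correlation between parameters is needed for this limit.

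**Step 4: covariate gain needed to restore 95% for AZD1061 Cmax.** With log variance cut by 5%, one-comparison power is 94.9-95.0%. With cuts of 22% and 23%, three-comparison power is 94.9% and 95.2%. So about 5% is needed for one comparison and about 22-23% for all three. In SD terms the first is 1 − sqrt(0.95) = 2.5% and the second about 12%.

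**The case against.** The strongest reply is that power is conventionally quoted per comparison, and that the singular CI in 11.4 most naturally means one interval. On that reading five of six parameters meet the figure and the sixth misses by about 1.2 points. This is right as far as it goes, and the per-comparison miss alone would be close to rounding. But 11.4 does not state that scope, and no section gives power for the rule that the study applies.

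Second, the planned model may remove variance. SAP 4.10.4 includes "treatment, injection site, anti-COVID-19 vaccination status (as reported on the CRF), and continuous baseline body weight on the log scale as fixed effects", and a cut of about 5% in log variance would close the one-comparison gap. This is plausible, but the documents state no reduction. That is why the 85% is called unadjusted.

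Third, the cap depends on the reading of the rule. If only the sum must pass, the single-mAb CVs do not settle the power, and the documents give no CV for the sum. If only the two co-formulation comparisons count, the cap is about 89%. Both points stand, which is why the analytes have to be named.

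A reader might infer more in three ways:
- *That chance failure is about three times as likely as stated.* This sets a joint risk of about 15% against a 5% that is best read as per comparison. Like for like, the risk for one comparison is about 6% against 5%.
- *That joint power is some specific value well below 85%.* This needs correlations between parameters, which the documents do not give. Independence is also doubtful, since Protocol 3.3.2 says "Measured serum AZD8895 and AZD1061 concentrations support that the PK of these mAbs are similar to each other".
- *That the error rate is affected.* Requiring every test to pass lowers power but does not inflate the type I error.

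**Conclusion.** Wrong as written, as a statement of power. On the plan's inputs, with the CVs taken as residual variability and no covariate gain, at least 95% is not met for AZD1061 Cmax even in one comparison (about 94%); it is met for the other five parameters (about 96% or more). It does not describe the rule in 11.1.1. If each mAb must pass all three comparisons, unadjusted power is at most about 85%, and at most about 89% for A-B and A-C only.

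The single-interval shortfall is small. The substantive fault is that the figure is offered as power to demonstrate comparability while the rule is joint and its analytes are unnamed. The documents do not support calling the study's conclusions unsafe: the point cannot produce a false finding of comparability, and the observed intervals will decide the result. It bears only on how a failure should be interpreted.

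**What to change.** In Protocol 11.4, the synopsis and SAP 4.12, replace the power sentence with wording such as:

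> With 69 evaluable participants per group, a true ratio of 1 and the Table 11-1 CVs taken as residual variability, power per parameter and per comparison is about 94% for AZD1061 Cmax and about 96% or more for each other parameter of the individual mAbs. For all three comparisons it is at most about 85% without covariate gain if each mAb must pass.

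In 11.1.1, name the analytes to which the rule applies. If only the sum must pass, state power from an observed CV of the sum instead of the last sentence above.

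Alternatively, keep 95%, but state the covariate variance reduction assumed and its source: about 5% of log variance for AZD1061 Cmax in one comparison, about 22-23% for all three.

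The cost is wording in three places and one clarification in 11.1.1. No extra enrolment is proposed, and the margin, model and alpha level stay unchanged.
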